Managing Chronic Pain Through the Web:
Evaluating the Efficacy of a Web-based Acceptance and Commitment Therapy (ACT)
Intervention

2018-10-15

One in five Canadians currently lives with chronic pain (CP; Reitsma et al., 2011) and the prevalence is expected to increase 70% by 2025 due to the aging population (Schopflocher, 2003). The daily experience of pain is often accompanied by important psychosocial changes. For example, CP has been associated with the onset of anxiety and depressive disorders (Gerrits et al., 2014) as well as feelings of anger and injustice (Scott et al., 2013). Research has also shown that a person with CP is twice more likely to commit suicide than a person without CP (Tang & Crane, 2006), which demonstrates the extent of suffering that people with this condition can experience.

At present, access to treatment for CP in Canada is limited (Lynch et al., 2011) and is considered a major challenge. For example, the average wait-list time for access to care is over a year in more than one third of publicly funded centres for pain and some could even go up to five years (Lynch et al., 2011; Peng et al., 2007). Furthermore, many areas of the country do not have interdisciplinary pain management centres (Lynch et al., 2011). Yet, access to pain management is a fundamental human right as stated in the Declaration of Montreal (Brennan et al., 2007; IASP, 2017). In addition to challenges associated to access to treatment for pain, medical/physical treatments are often not entirely effective in reducing one's pain when it is chronic. For example, only 30% of people who take pain-relief medication would see an improvement in their condition, while 70% of people continue to experience pain on a daily basis (Stahl, 2013).

Acceptance and Commitment Therapy ("ACT"; Hayes et al., 2012) is an empirically supported treatment with "strong research support" for CP by the *American Psychological Association* (APA, 2013). The experience of injustice has recently been conceptualized within the ACT psychological flexibility model (Scott et al., 2013b). ACT has been shown to help improve functioning and quality of life despite pain, and could potentially help mitigate the impact of perceived injustice on adverse pain outcomes (e.g. disability, depressive symptoms). Given the evidence of the effectiveness of ACT with CP, there are increasing efforts to improve the accessibility of this type of treatment. In particular, internet-delivered versions of ACT for CP are promising because they offer a cost-effective treatment option that usually requires little support from a therapist, and can be widely accessed.

Despite promising results (Bring, Åsenlöf, & Söderlund, 2016; Trompetter et al., 2016), further studies are needed to evaluate the effects of self-help interventions like ACT, including on physical and emotional functioning (Brown et al., 2016, Eccleston et al., 2014). Given the recent nature of self-help interventions in a population with chronic pain, other studies need to support their effectiveness. In addition, there are no studies that compared a self-help Web-based ACT intervention to a bibliotherapy intervention (French, Golijani-Moghaddam, & Schröder, 2017).

Objectives:

Evaluate the effectiveness and change processes of a web-based intervention program with minimal therapeutic contact, compared to a bibliotherapy and an education program based on brochures in adults with suffering of chronic pain.

Hypothesis 1: It is expected that the web-based self-help intervention generates a significant reduction in pain-related disability greater than the control group (education).

Hypothesis 2: It is expected that the bibliotherapy self-help intervention by bibliotherapy will result in a significant reduction in pain-related disability (primary variable) greater than the control group (education).

Hypothesis 3: It is expected that a web-based intervention will be associated with a greater reduction in pain-related disability (the primary variable) than bibliotherapy.

Hypothesis 4: It is expected that self-help Web-based interventions will lead to a significant improvement in the quality of life above the control (education) group.

Hypothesis 5: It is expected that bibliotherapy will significantly improved the quality of life superior to the control group (education).

Hypothesis 6: Self-help interventions are expected to result in a significant reduction in anxiety and depressive symptoms compared to the control (education) group.

Hypothesis 7: Self-help interventions with bibliotherapy are expected to result in a significant reduction in anxiety-depressive symptoms compared to the control (education) group.

Hypothesis 8: Results on primary (incapacity) and secondary variables (quality of life, anxiety-depression) will remain at 3 and 6 months and will be superior to education brochure (control group).

Hypothesis 9: The flexibility process is expected to be a mediator of change in the primary (disability) and secondary variables (quality of life, anode-depressive symptoms).

Participants and procedure: Recruitment will be done in collaboration with the Quebec Association of Chronic Pain (AQDC), the Quebec Pain Research Network (RQRD), the Quebec Society of Fibromyalgia (SQF), Migraine Quebec, the Pain Clinics of Quebec. Quebec (28 including the CHUM, distribution of maps and billboards) and social networks Facebook (Facebook page with paid advertising). Participants will be notified of the study via email. If they have an interest in the study, they will click on a link that will take them to the information and consent form and will be asked questions about the inclusion criteria.

- » Be over 18 years old Living in Quebec
- » Have a daily pain (greater than 4 out of 10) for more than three months that is not associated with cancer;
- » Have a reading and writing ability of French equivalent to a secondary 2;
- » Have Internet access at home and an email address;
- » Never have ACT-type psychotherapy or regular meditation in mindfulness, and have not read [name]'s book "Libérez-vous de pain par méditation et ACT";
- » Have a stable medication for at least one month, if necessary.
- » Being emotionally stable

If they do not meet the criteria, they will be refer to a resource page and will be asked to leave their name as needed to be referred to relevant resources. If people meet the inclusion criteria, they will be asked to complete the pre-test questionnaires, which will confirm their participation in the study.

Desis: A randomized control group trial with a sample of 300 presenting chronic pain, ie 100 persons for each experimental groups (web-based and bibliotherapy) and 100 persons for control group (education brochure).

Arms:

- Web-based, N = 100
- Bibliotherapy, N = 100
- Education brochure, N = 100

The estimate includes four measurement times (before and after the intervention, and two times at follow up (after 3 and 6 months) to assess the impact of the intervention in the longer term. The proposal will include three conditions, a group receiving a self-help web-based intervention, a group receiving a book-based intervention and a group receiving pain education brochures. Participants in all three groups receive 15-minute telephone calls from psychology students before and at week 3, a weekly email explaining the tasks to be completed, a discussion forum, access to an assistant to answer questions of a technical nature. These components aim to support participants' therapeutic approach and adherence to treatment (van Ballegooijen et al., 2014). Here is the content of the meetings for the 8 modules or weeks

Content of each module.

Week 1	Information about pain and ACT
Week 2	Values
Week 3	Learning to meditate

Week 4	Committed action
Week 5	Willingness to have pain
Week 6	Defuse from thoughts
Week 7	Pacing
Week 8	Conclusion

Instruments: All questionnaires will be self-administered online following an email sent. A hyperlink will automatically direct them to the UQTR Interactive Question Banking (IBQ) website. The completion time is evaluated between 25 and 30 minutes for each measurement period.

Participants answered questions related to socio-demographic information such as their age, education, daily occupation, and annual income. Participants also answered a series of questions related to pain, such as the diagnosis of chronic pain and the use of pain relief medication. Notably, participants were asked to rate the average pain they experienced in the past week on a numerical rating scale ranging from 0 (*no pain*) to 10 (*unbearable pain*). According to previous research, this scale is a reliable measure of pain intensity

Primary variable:

BPI; Brief Pain Inventory (Interference Scale). This 10-item questionnaire evaluates the severity and interference of pain in daily activities. On a Likert scale ranging from 0 = does not interfere to 10 = interferes completely, participants are asked to rate the degree to which pain interfered with various activities in the past week (e.g., social activities, work, mood, etc.). A higher average score represents higher levels of pain interference on daily function. Internal coherence of this scale is good ($\alpha = 0,88$).

Secondary variables:

Quality of life:

The World Health Organization Quality of Life-Brief (WHOQOL-BRIEF; WHOQOL; Group, 1998) is a self-reported measure of 26 items assessing quality of life in terms of physical and psychological health, social relationships and social functioning. environment. This instrument has demonstrated good levels of internal consistency for its subscales ($\alpha = .66$ to $\alpha = .80$) and adequate test-retest reliability ($r = .75$). The French version of the instrument offers high consistency (Baumann, Erpelding, Régat, Collin, & Briançon, 2010).

Anxiety and depression:

The Hospital Anxiety Depression Scale (HADS; Zigmond & Snaith, 1983; French version: Bocéréan & Dupret, 2014). This 14-item questionnaire evaluates psychological distress according to two 7-item subscale-measuring anxiety and depressive symptoms in non-psychiatric hospital contexts. Items are scored on a 4-point Likert scale ranging from 0 to 3. An example of items is “I feel tense or wound up.

Process measures:

Multidimensional Psychological Flexibility Inventory (24 items; MPFI). Psychological flexibility and inflexibility were measured with the French version of the MPFI-24 already described. This self-report questionnaire was developed by Rolffs, Rogge and Wilson (2016) and offers a response on a six-point Likert scale (Never / Always true). This tool has 12 distinct dimensions of flexibility or psychological influence (6 minutes).

Chronic Pain Self-Efficacy Scale (FC-CPSES, 6 items). Self-efficacy is an important aspect to consider when evaluating the benefits of an intervention to improve self-management of chronic pain. This instrument has an internal consistency evaluated at more than $\alpha = 0.86$. Better self-efficacy scores are associated with a better quality of psychological life, less severe pain symptoms and less dramatic tendencies ($P < 0.05$), which supports the convergent validity of this tool (2 min).

Chronic Pain Acceptance Questionnaire (CPAQ-8; McCracken, Vowles, & Eccleston, 2004; French version: Scott, Bernier, Garland, & Sullivan, 2003). The CPAQ-8 assesses a person’s acceptance of the experience of pain using two four-item subscales: activity engagement, which evaluates the degree to which behaviours are limited or restricted by pain, and pain willingness, which evaluates the degree or effort directed at controlling pain. Items are scored on a 7-point Likert scale ranging from 0 = never true to 6 = always true. An example of items is “I am getting on with the business of living no matter what my level of pain is.” Scores for the pain willingness subscale must be reversed before calculating a total score.

Questionnaire filled each week:

Weekly journal (7 items):

Participants will be invited to answer this short questionnaire before accessing the contents of the module for the week. It is an abbreviated tool with 3 items on a Likert type scale (0 = never, 6 = always) that assess flexibility processes (open, aware and active). In addition, to assess dependent variables throughout the process, 4 questions measuring disability, pain intensity, depression, and anxiety were added to the questionnaire. Thus, this questionnaire includes a total of 7 items designed to measure the evolution of the variables of interest over time, and the completion time is evaluated at 2 minutes.

Follow up only:

The Satisfaction Questionnaire (QS-8, Sabourin, Pérusse, & Gendreau, 1989) is the French version of Client Satisfaction Questionnaire-8 (CSQ-8, Larsen, Atkinson, Hargreaves, & Nguyen, 1979). This instrument is a self-reported eight-item measure to assess satisfaction with health care services. The response format is Likert type (1 to 4). A high total score indicates greater satisfaction. He demonstrated good internal consistency ($\alpha = .89$) (Sabourin, et al., 1989).

System Usability Scale (SUS; Brooke, 1996) is a usability questionnaire that has been adapted into French. It will be sent to participants in the Web-based intervention only after the eight weeks of the program in order to measure their level of satisfaction with the program. This questionnaire contains 10 items (eg: I find that the features of this online workshop are well integrated) and responds on a five-point Likert scale (not at all strongly agree). A question will be added to ask participants about the number of modules they have completed. This questionnaire will take less than two minutes to complete.

Follow up only (week 20 and 28):

Patient Global Impression of Change (PGIC, 5 items). This tool assesses the level of change in pain, functioning, quality of life and psychological well-being factors over the past three months. They are evaluated on a 7-point Likert scale from 0 (significantly increased) to 6 (significantly decreased). A fifth item evaluates pain relief in the past three months and is measured on an ordinal scale ranging from 0 (no relief) to 100 (complete relief). This tool is increasingly used to assess the impact of change in the lives of patients with chronic pain (1 minute).

Data analysis:

The sample size for this study is optimized to compare the expected results on post-treatment pain interference. In addition, we expect the effect size for the web-based group to be higher than for the bibliotherapy. Randomized trials using an ACT intervention for chronic, web-based pain reported effect sizes of $d = 0.33$ (Trompetter et al., 2014), $d = 0.56$ (Buhrman et al., 2013) and $d = 0.58$ (Lin et al., 2017) with respect to pain-related interference. Considering the attrition of about 25% (between pretest and stimulus), based on the calculations of Lin et al. (2014), to obtain a statistical power of 80% (5%) and to detect an average effect size ($d = 0.40$), which proves clinically satisfactory for this type of study, a sample of 100 participants per group (300 in total) is required according to our calculations on G^* power.

Generalized linear models with a group-by-time interaction will be used to compare the time conditions of the ACT-guided group with bibliotherapy and education brochures. Dichotomous arrival points will be modelled using a binomial distribution and a log link while a normal distribution and identity link will be used in the case of continuous arrival points. The generalized estimating equations approach will take into account the correlation between measurement times. Contrasts, defined a priori based on research hypotheses, will be used to make comparisons between groups and different measurement times. The analyzes will be performed according to the intent to treat.

Considering the current waiting lists for accessing psychological services in the public system, the social relevance of developing the accessibility of a self-help intervention by the Web is undeniable. We hope that our statistical data will support the development of new practices in the management of patients with chronic pain. The innovation will provide access to effective therapy in a short time and at low cost with a cost-benefit ratio.

References

- American Psychological Association (2013). Chronic or persistent pain. Retrieved from <http://www.div12.org/psychological-treatments/disorders/chronic-or-persistent-pain>
- Bender, J. L., Radhakrishnan, A., Diorio, C., Englesakis, M., & Jadad, A. R. (2011). Can pain be managed through the Internet? A systematic review of randomized controlled trials. *Pain*, 152(8), 1740-1750.
- Bergeron, D. A. (2016). Effects of an Internet-delivered cognitive behavioural therapy programme on chronic pain patients. *Evidence-Based Nursing*; 2016 Jul, Vol 19 (3), pp 87, Electronic publication. doi:10.1136/ebnurs-2016-102305
- Boggs, M. J., Beck, A., Felder, N. J., Dimidjian, S., Metcalf, A. C., & Segal, V. Z. (2014). Web-Based Intervention in Mindfulness Meditation for Reducing Residual Depressive Symptoms and Relapse Prophylaxis: A Qualitative Study. *J Med Internet Res*, 16(3), e87. doi:10.2196/jmir.3129

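### The secondary and follow-up claims in Hypotheses 4 to 8 do not depend on the arm's primary result and are not labelled supportive, so a programme that fails on disability can still claim a pre-specified benefit

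*Combined protocol and SAP*

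**What the plan says.** All references are to the combined protocol and SAP.

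- **Objectives, Hypotheses 1 to 3.** These concern pain-related disability, the primary variable: web against education, bibliotherapy against education, and web against bibliotherapy.
- **Objectives, Hypotheses 4 and 5 (quality of life).** The web programme "will lead to a significant improvement in the quality of life above the control (education) group", and "bibliotherapy will significantly improved the quality of life superior to the control group (education".
- **Objectives, Hypotheses 6 and 7 (anxiety and depressive symptoms).** Both predict a significant reduction against education. Hypothesis 7 names bibliotherapy, so Hypothesis 6 is read here as the web arm.
- **Objectives, Hypothesis 8.** Results on the primary and the secondary variables "will remain at 3 and 6 months and will be superior to education brochure (control group".
- **Instruments.** BPI interference is listed as primary. Quality of life (WHOQOL) and anxiety and depression (HADS) are headed as secondary.
- **Data analysis.** "Contrasts, defined a priori based on research hypotheses, will be used to make comparisons between groups and different measurement times". The sample size is set for post-treatment pain interference only. Its sentence holds the sole error level, 5%, with no statement of sidedness.

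No section gives a multiplicity adjustment, a testing order, a condition tied to Hypotheses 1 to 3, or an exploratory or supportive label for Hypotheses 4 to 8. The hypotheses are numbered, but the numbering is not described as a test sequence.

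**The concern.** Calling a variable secondary ranks it. It does not say what may be claimed for it when the primary comparison fails. Hypotheses 4 to 7 carry the same language of significance as Hypotheses 1 and 2, and the plan turns hypotheses into a priori contrasts. If an arm shows no effect on disability but reaches p < 0.05 on quality of life or mood, the report can present that as confirmation of a numbered, pre-specified hypothesis. There are several such chances, and nothing in the plan limits them.

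The closing paragraph of Data analysis hopes that the results will support new practices in managing chronic pain. A chance secondary finding could then be used to promote a programme that did not work on its main target. The point concerns the secondary and follow-up claims only, not the three primary contrasts.

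**Working it through.** **The plan's own figure.** The documents state no error rate for a family of tests. The only calculation that uses the 5% is the sample size, with d = 0.40, 80% power and about 25% attrition.
- Two-sided: n = 2(1.960 + 0.842)² / 0.40² = 98.1, so 99 per group. This agrees with the stated 100 only if attrition is ignored; 99 / 0.75 = 132.
- One-sided: n = 2(1.645 + 0.842)² / 0.40² = 77.3, so 78 per group; 78 / 0.75 = 104, or 78 × 1.25 = 97.5.

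The calculation therefore does not settle the sidedness. Two-sided 5% is assumed below, which is 2.5% per test in the direction of benefit. Whether 100 per group is adequate is a separate matter.

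**Counting the contrasts, with one score per construct.**
- Hypotheses 4 to 7: 2 arms × 2 outcomes = 4.
- Hypothesis 8, if each part is read separately: 2 arms × 3 outcomes × 2 times = 12. Of these, 2 × 2 = 4 are on disability, the primary variable.
- Hypotheses 4 to 8: 4 + 12 = 16, of which 12 are on secondary outcomes.

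**If the tests were independent.** P(at least one false benefit) = 1 − 0.975^k. For k = 4 this is 9.6%; for k = 16 it is 33%. The contrasts are positively correlated, so these figures are too high.

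**Allowing for correlation.** Contrasts were simulated as multivariate normal with no true differences between arms and a critical value of 1.96.
- Between the two arm-versus-education contrasts the correlation is 0.5. This follows from the shared control with equal groups ("a sample of 100 participants per group (300 in total) is required").
- Between outcomes it is assumed to be 0.3 to 0.7, central value 0.5.
- Between measurement times it is assumed to be 0.5 to 0.8, central value 0.7.

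The documents give neither of the last two.

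| Both programmes ineffective, false benefit only | Central | Range |
|---|---|---|
| Hypotheses 4 to 7 (4 contrasts) | 8.1% | 7.4 to 8.5% |
| Hypothesis 8 alone, read as 12 contrasts | 17.5% | 14 to 21% |
| Hypotheses 4 to 8 (16 contrasts) | 20.5% | 16 to 25% |
| Hypotheses 4 to 8, secondary outcomes only (12) | 16.5% | 14 to 20% |
| False benefit in Hypotheses 4 to 7, none of Hypotheses 1 to 3 succeeding | about 6% | 5 to 7% |

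**One programme alone.** Its two contrasts in Hypotheses 4 to 7 give about 4.6% (range 4.2 to 4.8%). With its six contrasts from Hypothesis 8 the figure is about 12%.

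**Score choice.** The plan does not say whether the HADS total or its two subscales are tested. Testing the subscales separately raises the figure for Hypotheses 4 to 7 to about 10 to 12%.

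**With the claims opened by the arm's own primary result.** A secondary claim counts only if that arm's post-treatment BPI contrast is also significant. The rate for Hypotheses 4 to 7 falls from 8.1% to about 1.5% (range 0.8 to 2.3%). For all of Hypotheses 4 to 8 it falls to about 3%.

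**The case against.** The strongest reply is that a hierarchy already exists. The plan separates primary from secondary variables, Hypothesis 8 repeats the distinction, and the trial is sized on post-treatment interference alone. A careful reader can tell a secondary result from a primary one, and formal error control over labelled secondary outcomes is partly a matter of preference in a trial of this kind. This stands as far as it goes: a full alpha-splitting scheme is not required. It does not supply the missing rule on what may be claimed when the primary contrast fails.

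Four stronger readings are tempting, and the documents do not support them.

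- *A single ineffective programme has an 8 to 21% chance of a false secondary benefit.* Those figures need both programmes to be ineffective. One alone gives about 4.6%, or about 12% with its follow-up contrasts.
- *The figure of about 20% is a rate for secondary outcomes.* Four of its 16 contrasts are disability at follow-up. Secondary outcomes alone give about 16.5%.
- *Hypothesis 8 is 12 separate claims with no link to the post-treatment result.* It is one sentence, and saying that results will remain presupposes an earlier effect. If all its parts must succeed together, it adds no inflation. The plan does not say which reading applies.
- *The plan declares these tests confirmatory at the full 5%.* It uses neither expression for them. The 5% is inferred from the sample-size sentence, although no other level is given.

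**Conclusion.** The concern holds in a limited form. Hypotheses 4 to 8 are worded as significant or superior benefits, and nothing ties them to the arm's primary result or labels them supportive.

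The firm figure is about 8% for at least one false benefit in Hypotheses 4 to 7 when both programmes are ineffective, against 2.5% for one test. In about 6% of such trials, that false benefit appears although none of Hypotheses 1 to 3 succeeds. The figure of about 20% for Hypotheses 4 to 8 applies only if Hypothesis 8 is tested piece by piece.

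All these rates rest on two-sided 5% per contrast, one score per construct, and assumed correlations between outcomes and times. The primary comparisons are unaffected. The change is worth making because the gap is clear and inexpensive to close.

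**What to change.** Add to the Data analysis section:

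> Hypotheses 4 to 8 support an efficacy claim for an arm only if that arm's post-treatment BPI interference contrast against education is significant. Otherwise they are reported as estimates with 95% confidence intervals and labelled exploratory. The 3- and 6-month contrasts of Hypothesis 8 are interpreted as maintenance of an effect shown post-treatment.

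Reword Hypotheses 4 to 8 in the Objectives to match.

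This costs a few sentences and needs no new data or participants. Tests in an arm that passes keep their full level. The price is that a secondary or follow-up effect in an arm whose primary contrast fails can be reported only as exploratory. To show its size, assume d = 0.40 and 75 completers per arm (100 × 0.75). A simple two-group test then has power Φ(0.40 × √(75/2) − 1.96) = Φ(0.49), about 69%. An arm with the planned effect would therefore miss the condition in about 31% of trials. Adjustment for baseline would reduce that.

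Two stricter rules are optional and a matter of preference. A fixed order with web before bibliotherapy is costly: if bibliotherapy's claims also require both primary contrasts against education to succeed, its last test would be reached and passed in only about 28% of trials, assuming d = 0.40 on every outcome and 75 completers per arm. Treating every contrast in Hypothesis 8 as exploratory would give up long-term claims even where the primary contrast succeeds.

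### With 25% attrition, 100 per arm gives about 68% power for d = 0.40 on a two-sided unadjusted test, not the stated 80%

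*Combined protocol and SAP*

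**What the plan says.** The sample-size paragraph under Data analysis names its target: "The sample size for this study is optimized to compare the expected results on post-treatment pain interference". It then gives its inputs. Attrition enters with "Considering the attrition of about 25% (between pretest and stimulus"; power and significance level enter with "to obtain a statistical power of 80% (5%) and to detect an average effect size", the effect being d = 0.40. The result is that "a sample of 100 participants per group (300 in total) is required according to our calculations" in G*Power. The G*Power test family, the sidedness and any correlation between measurements are not given.

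The design paragraph makes the same figure the size of the whole trial: "A randomized control group trial with a sample of 300 presenting chronic pain", split 100 / 100 / 100. Under Participants and procedure, completing the pre-test questionnaires is what confirms a person's participation.

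The hypotheses are directional in wording; Hypothesis 1, for example, expects that the web programme "generates a significant reduction in pain-related disability greater than the control group (education"). No one-sided test is specified. For the analysis, the plan names a group-by-time model and says "The generalized estimating equations approach will take into account the correlation between measurement times". It adds: "Contrasts, defined a priori based on research hypotheses, will be used to make comparisons between groups and different measurement times". It does not say which contrast the sample size refers to, what working correlation is used, or whether baseline is a covariate.

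**The concern.** The paragraph says attrition was taken into account, yet 100 per arm is the usual two-sided t-test answer for d = 0.40 with nobody lost. If a quarter of participants give no post-treatment score, the trial has less power than it claims.

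This calculation is the plan's only justification for 300 participants. At 68% power, the chance of missing a true effect of the size the plan calls clinically satisfactory is about 32% instead of 20%. A null result could then be read as evidence of no benefit from a trial described as having 80% power. The lowest effect the plan cites from earlier web-based ACT trials, d = 0.33, is below both 0.40 and the effect that 75 per arm can detect with 80% power.

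**Working it through.** **Inputs from the plan:** d = 0.40 (so SD = 1), 5% level, 80% power, 25% attrition, 100 per arm, equal allocation. **Assumed, because not stated:** two-sided test, two-arm comparison of post-treatment means, no multiplicity adjustment. All powers use the noncentral t distribution.

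**1. Reproducing the stated 100.** With n analysed per arm, the noncentrality is d × √(n/2) on 2n − 2 degrees of freedom. Solving for 80% power, two-sided 5%, gives n = 99.08, so 100 per arm. That matches the plan's figure before any loss. At n = 100 the power is 80.4%.

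**2. Applying the stated attrition.** 100 × (1 − 0.25) = 75 per arm. The noncentrality is 0.40 × √(75/2) = 2.449 on 148 degrees of freedom, and power is **68.2%**. Intermediate losses give 76.1% (10% lost, n = 90) and 71.0% (20% lost, n = 80). Solving the other way, 75 per arm has 80% power for **d = 0.46**. To keep 80% for d = 0.40 on this test, enrolment would have to be 100 / 0.75 = 133.3, so 134 per arm (402 in total).

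**3. One-sided 5%.** The requirement is 77.97, so 78 analysed, and 78 / 0.75 = 104 enrolled. At 75 per arm power is 78.6%, and 80% is reached at d = 0.41.

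**4. Using the baseline score.** Let r be the pre-post correlation of the BPI interference score. The plan gives no value, so r is an assumption throughout. Equal variances at both times are assumed. Where all baselines are kept, dropout is also assumed unrelated to outcome. Variance per arm of the quantity compared, with 75 post-treatment values per arm:

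- Baseline-adjusted: (1 − r²)/75
- Change, completers only: 2(1 − r)/75
- Change, all 100 baselines kept and the correlation modelled: (1 − r²)/75 + r²/100 + 1/100 − 2r/100
- Change, GEE with independence working correlation: 1/75 + 1/100 − 2r/100

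The standard error of the difference is the square root of twice this value. For example, the third formula at r = 0.5 gives 0.0125, and √0.025 = 0.1581.

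| Two-sided contrast | r = 0.4 | r = 0.5 | r = 0.6 | r for 80% |
|---|---|---|---|---|
| Baseline-adjusted | 75.7% | 80.2% | 86.0% | 0.50 |
| Change, all baselines | 63.7% | 71.0% | 79.7% | 0.60 |
| Change, completers | 60.3% | 68.2% | 77.7% | 0.62 |
| Change, independence GEE | 62.1% | 68.2% | 75.2% | 0.66 |

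With all baselines kept, the change contrast equals the unadjusted 68.2% at r = 0.46 and is weaker below that. Repeated measures therefore do not guarantee a gain. If the test were one-sided, 80% would be reached at r = 0.20 (adjusted), 0.49 (change, all baselines) and 0.52 (change, completers).

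**The case against.** The strongest reply is that 68% belongs to a test the plan never names. The planned analysis is a group-by-time GEE model with contrasts, and its power could be lower or higher than 68%. This is true, and it limits the claim: 80% is not shown to be impossible. But the plan sizes the trial on a post-treatment comparison and gives no correlation or baseline adjustment that would make the gain calculable.

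A second reply is that another route leads to about 100. The directional hypotheses may imply a one-sided test, and 77.97 × 1.25 = 97.5, or 98, which rounds to 100 with attrition included. This is a plausible reconstruction, so the omission of attrition is not proved. It does not rescue the figure in full: multiplying by 1.25 does not offset a 25% loss, 75 analysed per arm still gives 78.6%, and no sidedness is stated. On that route, however, the shortfall is 1.4 points instead of about 12.

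A third reply concerns the attrition wording, which literally places the loss between the pre-test and the stimulus, and the plan does not say when randomisation occurs. If that loss preceded allocation and 100 were the number allocated, 80% would hold apart from later loss. But completing the pre-test is what confirms participation, and 300 is given as the sample, so loss counted from the pre-test comes out of the 100. The wording should still be clarified.

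Finally, analysis by intention to treat does not by itself recover unobserved scores, and the plan states no imputation.

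**Conclusion.** The concern holds. On the plan's own inputs, a two-sided unadjusted post-treatment comparison has about 68% power for d = 0.40, not 80%, and 80% power only for d = 0.46. This rests on 75 analysed per arm, a two-sided 5% level and no multiplicity adjustment. An unstated one-sided test brings power to 78.6%. Unstated two-sided alternatives reach 80% only with a correlation of about 0.50 (baseline-adjusted) or 0.60 to 0.66 (change contrasts). That attrition was left out is a reasonable inference from the exact match at 100, but not established. What is established is that the stated power is not delivered on the conventional reading and cannot be verified on any other. This must be corrected, because the trial's size rests on it.

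**What to change.** Keep 300 and do one of the following.

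- **Restate the power.** Say that 100 are randomised per arm, that about 75 are expected to have post-treatment data after 25% attrition, and that this gives about 68% power for d = 0.40 (two-sided 5%, unadjusted post-treatment comparison), or 80% power for d = 0.46.
- **Keep the 80% claim.** Prespecify the two-sided baseline-adjusted post-treatment contrast as the primary contrast of the planned model, and state the assumed pre-post correlation of the BPI interference score (at least about 0.5) with its source.

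In either case, give the G*Power test, the sidedness and the contrast the power refers to. State that 100 is the number randomised, not the number analysed, and clarify the interval over which the 25% loss is counted. If the original calculation used other inputs, reporting them would let the 80% be checked.

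The cost is two or three sentences in the Data analysis section and no extra participants. The downside is either a less favourable stated power or an advance commitment to one contrast and one correlation.
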